#### Re-start of NA treatment:

- immediately with signs of decreasing liver function based on laboratory findings (eg, INR, direct bilirubin) or clinical assessment (eg, ascites, hepatic encephalopathy)
- immediately with an HBV DNA value of >100,000 IU/mL (irrespective of confirmation and/or ALT increase)
- with confirmed post-treatment HBeAg seroreversion (HBeAg positive after it was negative at NA completion)
- with confirmed\* post-treatment increases in HBV DNA >2,000 IU/mL and ALT >5x ULN
- With confirmed\* post-treatment increases in HBV DNA >20,000 IU/mL

Note: Additional re-testing and/or earlier restarting of NA-treatment is at the investigator's discretion also if the above cut-offs are not yet met.

\* At least 4 weeks apart – frequency of visits as described above

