## 1. INTRODUCTION

This statistical analysis plan (SAP) for the 73763989PAHPB2005 phase 2 trial describes the statistical analyses and definitions to assess the efficacy and safety of study interventions including JNJ-73763989, pegylated interferon alpha-2a (PegIFN- $\alpha$ 2a), Nucleos(t)ide analogs (NA) regimen with or without JNJ-56136379 in patients with HBeAg positive chronic hepatitis B (CHB) virus infection and ALT  $\leq$ 2x ULN who are not currently being treated for their HBV infection (i.e., who had <9 months of prior treatment which ended at least 12 months before screening, including treatment-naïve patients). In the rest of the document the abbreviations JNJ-3989 and JNJ-6379 are used to refer to the treatments JNJ-73763989 and JNJ-56136379, respectively. JNJ-6379 was initially part of the study intervention but has been removed as study intervention with the implementation of an urgent safety measure, as described in Protocol Amendment 6.

This study is part of the platform trial PLATFORMPAHPB2001 in participants with CHB. The protocol amendment for 73763989PAHPB2005 constitutes the Intervention Specific Appendix that describes all the specific and/or additional features of this study complementing the common design elements of the platform trial described in the Master Protocol.

This SAP is to be interpreted in conjunction with the clinical protocol Amendment-6 finalized on 30 September 2021, and with the Master Protocol Amendment-3 for PLATFORMPAHPB2001 finalized on 21 January 2021.

Details of the pharmacokinetic (PK) and pharmacokinetic/pharmacodynamics (PK/PD) analyses will be described in a separate analysis and modeling plan.

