### 5.3.1.1.2.2. NA Re-Treatment Criteria and Monitoring After Stopping of NA

Participants who meet the NA treatment completion criteria will be monitored closely during the follow-up phase.

After stopping NA treatment, participants should be monitored as follows:

- Regular monitoring visits will be every 4 weeks during the follow-up phase in accordance with the schedule of activities.
- A post-treatment HBV DNA value of >20,000 IU/mL should trigger re-testing of ALT/aspartate aminotransferase (AST), HBV DNA, and total and direct bilirubin within a maximum of 7 days from receipt of the data and further repeats as necessary (i.e., weekly until HBV DNA returns to <20,000 IU/mL).
- A post-treatment HBV DNA value of >2,000 IU/mL (but <20,000 IU/mL) should trigger a re-test within 14 days from receipt of the data and further repeats as necessary (i.e., every other week until HBV DNA returns to <2,000 IU/mL).
- A post-treatment ALT value of >5x ULN should trigger re-testing of ALT, AST, alkaline phosphatase (ALP), total and direct bilirubin, International Normalized Ratio (INR), albumin, and HBV DNA on a weekly basis until ALT and AST levels have returned to <5x ULN.

After stopping NA treatment, participants should re-start NA treatment:

- Immediately with signs of decreasing liver function based on laboratory findings (eg, INR, direct bilirubin) or clinical assessment (e.g., ascites, hepatic encephalopathy).
- Immediately with an HBV DNA value of >100,000 IU/mL (irrespective of confirmation and/or ALT increase).
- With confirmed post-treatment HBeAg seroreversion (HBeAg positive after it was negative at NA completion).
- With confirmed\* post-treatment increases in HBV DNA >2,000 IU/mL and ALT >5x ULN.
- With confirmed\* post-treatment increases in HBV DNA >20,000 IU/mL.

*\*At least 4 weeks apart – frequency of visits as described above.*

**Note:** Additional re-testing and/or earlier restarting of NA treatment is at the investigator's discretion, even if the above cut-offs are not yet met.

In case NA treatment is re-started, participants will be followed until the end of the study or until clinical stabilization, whichever comes later.

Participants who actually re-started NA treatment and monitoring after stopping of NA will be identified based on the 'Study Drug Administration for NA' CRF page.

Participants who meet the NA re-treatment criteria will be identified based on the CRF page of 'NA Re-treatment Criteria Assessment'.

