48	Participant missed JNJ-6379: more than 5 doses or 3 consecutive doses within a four week period <specify number of missed dose/consecutive dose> within <specify duration of missed dose>.	Received wrong treatment or incorrect dose	If classified as major protocol deviation, excluded from PP set.
48.1	Participant was administered (a) dose(s) of JNJ-6379 after approval of CTPA6.	Received wrong treatment or incorrect dose	If classified as major protocol deviation, excluded from PP set.
49	Participant missed NA treatment for more than 5 doses within a four week period. <specify number of missed dose> within <specify duration of missed dose>.	Received wrong treatment or incorrect dose	If classified as major protocol deviation, excluded from PP set.
50	Participant missed 2 or more PegIFN- $\alpha$ 2a doses <specify number of missed dose>.	Received wrong treatment or incorrect dose	If classified as major protocol deviation, excluded from PP set.
51	Participant received expired study medication <JNJ-3989/ JNJ-6379/ NA/ PegIFN- $\alpha$ 2a>.	Other	If classified as major protocol deviation, excluded from PP set.
52	Study treatment <JNJ-3989, JNJ-6379/ NA/ PegIFN- $\alpha$ 2a> was not <prepared/ handled/ stored> in line with intervention-specific pharmacy manual/ study site investigational product and procedures manual <specify the incorrect preparation/handling/storage conditions>.	Other	If classified as major protocol deviation, excluded from PP set.
52.1	Study treatment <JNJ-3989, NA/ PegIFN- $\alpha$ 2a> was not <prepared/ handled/ stored> in line with intervention-specific pharmacy manual/ study site investigational product and procedures manual <specify the incorrect preparation/handling/storage conditions>.	Other	If classified as major protocol deviation, excluded from PP set.
53	Participant has event of "signs of decreasing liver function" based on laboratory or clinical findings but did not start NA treatment.	Received wrong treatment or incorrect dose	If classified as major protocol deviation, excluded from PP set.

Sequence No.	Protocol Deviation Description (DVTERM)	Protocol Deviation Coded Term (DVDECOD)	Exclude from PP
53.1	Participant has event of "signs of decreasing liver function" based on laboratory or clinical findings or HBV DNA value of >1,000,000 IU/mL (irrespective of confirmation and/or ALT increase) but did not start NA treatment.	Received wrong treatment or incorrect dose	If classified as major protocol deviation, excluded from PP set.

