54	Participant has confirmed HBeAg seroreversion but did not start NA treatment.	Received wrong treatment or incorrect dose	If classified as major protocol deviation, excluded from PP set.
55	Participant has a confirmed post-treatment increase in HBV DNA >2,000 IU/mL and ALT >5 x ULN over a period of at least 4 weeks, but did not start NA treatment.	Received wrong treatment or incorrect dose	If classified as major protocol deviation, excluded from PP set.
55.1	Participant has a confirmed post-treatment increase in HBV DNA >2,000 IU/mL and ALT >5 x ULN over a period of at least 4 weeks, but did not start NA treatment.	Received wrong treatment or incorrect dose	If classified as major protocol deviation, excluded from PP set.
56	Participant has a confirmed post-treatment increase in HBV DNA >20,000 IU/mL over a period of at least 4 weeks, but did not start NA treatment.	Received wrong treatment or incorrect dose	If classified as major protocol deviation, excluded from PP set.
57	Participant has received a Covid-19 vaccine on the same day as PegIFN- $\alpha$ 2a administration.	Other	If classified as major protocol deviation, excluded from PP set.
58	Patients met at least one criteria of discontinuation of study intervention but did not stop	Developed withdrawal criteria but not withdrawn	Yes
71	<Specify study specific procedure(s)> <was/were> conducted prior to signing an informed consent form.	Other	If classified as major protocol deviation, excluded from PP set.
72	<Specify screening procedure(s)> <was/were> not performed within <28 days or 42 days> before first study drug administration.	Other	If classified as major protocol deviation, excluded from PP set.
73	Screen failed Participant was rescreened without agreement with the sponsor.	Other	If classified as major protocol deviation, excluded from PP set.
74	Study <specify the visit which> procedure not done at scheduled Visits.	Other	If classified as major protocol deviation, excluded from PP set.
75	Efficacy evaluation <specify assessment> not done at scheduled Visits.	Other	If classified as major protocol deviation, excluded from PP set.
76	Study Visits <specify visit> not performed per protocol.	Other	If classified as major protocol deviation, excluded from PP set.
77	Potential confusion between cross-over sites participating in REEF-studies.	Other	If classified as major protocol deviation, excluded from PP set.

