78	Site reported protocol deviation not specified elsewhere.	Other	If classified as major protocol deviation, excluded from PP set.
79	<Specify visit(s)>: <specify blood, serum or urine, e.g., PK Samples, PMBC Sample> sample were collected in error however not destroyed.	Other	If classified as major protocol deviation, excluded from PP set.
80	Study Visits <specify visit> not performed per protocol.	Other	If classified as major protocol deviation, excluded from PP set.

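### SAP Attachment 1 row 53.1 gives the immediate NA-restart trigger as >1,000,000 IU/mL HBV DNA, ten times the figure in the protocol and in SAP 5.3.1.1.2.2, so unsustained values between the two figures have no specific deviation code

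*SAP*

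**What the plan says.** SAP Attachment 1 lists the major deviations used to build the per-protocol set. The second limb of row 53.1 covers a participant with an "HBV DNA value of >1,000,000 IU/mL (irrespective of confirmation and/or ALT increase) but did not start NA treatment". Its consequence is conditional: "If classified as major protocol deviation, excluded from PP set".

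SAP 5.3.1.1.2.2 gives the restart rule as "Immediately with an HBV DNA value of >100,000 IU/mL (irrespective of confirmation and/or ALT increase"). Protocol Appendix 16 reads "immediately with an HBV DNA value of >100,000 IU/mL (irrespective of confirmation and/or ALT increase"), and the protocol synopsis, 4.2 and 6.6.2 carry the same figure.

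Neighbouring rows cover the other restart criteria:
- Row 53 and the first limb of row 53.1: declining liver function.
- Row 54: confirmed HBeAg seroreversion.
- Rows 55 and 55.1: "Participant has a confirmed post-treatment increase in HBV DNA >2,000 IU/mL and ALT >5 x ULN over a period of at least 4 weeks".
- Row 56, on viral load alone: "Participant has a confirmed post-treatment increase in HBV DNA >20,000 IU/mL over a period of at least 4 weeks, but did not start NA treatment".

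Row 78 is a catch-all: "Site reported protocol deviation not specified elsewhere". SAP 4.5 bases major deviations on clinical review and does not treat its listed criteria as exhaustive. The preamble to Attachment 1 says the list is still to be brought into line with the protocol amendment and finalised before the primary analysis database lock.

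SAP 1 states: "This SAP is to be interpreted in conjunction with the clinical protocol Amendment-6". The protocol supplied is Amendment 7.

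**The concern.** One trigger carries two figures in text that is currently in force. Row 53.1 repeats even the qualifier that neither confirmation nor an ALT rise is needed, so it is plainly meant to mirror the restart rule and not to set a separate, looser test.

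Anyone programming the deviation check from Attachment 1 would apply a different rule from the one the sites were given. Some participants whom the protocol text required to restart at once would then not be coded under the row written for that purpose. The protocol explains in 2.3.3 and 4.2 that these criteria were tightened after severe events following NA withdrawal, so the accuracy of this code bears on the reporting of a safety rule as well as on membership of the per-protocol set.

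**Working it through.** No sample size, power or interval is involved. The check compares thresholds and then applies the rules to example cases.

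**Size of the gap.** Row 53.1 uses >1,000,000 IU/mL. Protocol 6.6.2 and SAP 5.3.1.1.2.2 use >100,000 IU/mL. The ratio is 1,000,000 / 100,000 = 10, and log10(10) = 1. The affected values are those above 100,000 and up to 1,000,000 IU/mL.

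**Whether the other rows agree.** Protocol 6.6.2 has five restart criteria. Four appear in Attachment 1 without conflict: liver function (rows 53 and 53.1), HBeAg seroreversion (54), HBV DNA >2,000 IU/mL with ALT >5x ULN (55 and 55.1), and confirmed HBV DNA >20,000 IU/mL (56). Only the immediate HBV DNA criterion differs.

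**What is caught.** Take a participant off NA who does not restart and has no liver signs, no HBeAg seroreversion and no ALT >5x ULN. The rules applied are immediate restart (>100,000, unconfirmed), row 53.1 (>1,000,000, unconfirmed) and row 56 (>20,000, sustained over at least 4 weeks).

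| HBV DNA (IU/mL) | Restart required by protocol text | Row 53.1 | Row 56 |
|---|---|---|---|
| 500,000 once, no later confirmation | Yes | No | No |
| 500,000 twice, at least 4 weeks apart | Yes | No | Yes |
| 500,000, then 15,000 | Yes | No | No |
| 2,000,000 once | Yes | Yes | No |

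The first and third cases are the gap: values between the two figures that are not sustained and meet no other listed criterion. The second case lies in the same range but is coded by row 56.

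**Whether another output fills the gap.** SAP 5.3.2.1.1.2 plans a cross-tabulation of restarted or not against criteria met or not, and a listing of those who met the criteria with their restart status. Both rest on an overall CRF flag. The SAP Amendment 2 history says that counts by individual sub-criterion were dropped because the CRF does not hold them. These outputs can show a missed restart but not which criterion was missed.

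**How many could be affected.** The SAP Amendment 4 history reports one participant who qualified to complete NA and came off it at consolidation Week 12. For scale, against the planned total of about 60 participants this is 1/60 = 1.7%. It is not a strict upper bound, because protocol 4.1 and 7.1 allow NA to be stopped in consultation with the sponsor after early discontinuation of JNJ-3989. The documents do not show anyone with a value between the two figures.

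**The case against.** The strongest counter-argument is that the mismatch changes almost nothing. Row 56 picks up any rise in the range that lasts at least 4 weeks. Protocol 6.6.2 requires weekly re-testing above 20,000 IU/mL, so a lasting rise would be documented repeatedly. Row 78 and the open wording of SAP 4.5 leave a route for the remainder. Missed restarts are tabulated and listed independently of Attachment 1. Row 53.1 excludes nobody automatically, the primary analysis uses the ITT set, no formal test is done (SAP 5.1.1), and the per-protocol result is an observed-case count and percentage (SAP 5.2.4).

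Most of this stands, and it limits the point to a specific missing code. It does not remove the contradiction. Row 78 depends on a site reporting the event, SAP 4.5 supplies no threshold, and the listing does not identify the criterion.

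Three stronger readings are tempting but not supported:
- A reader might infer that every missed restart between the two figures goes unflagged and is never considered for the per-protocol set, or that safety deviations are under-reported overall. Row 56, the other rows and the separate listing contradict this.
- A reader might infer that 1,000,000 is a typing error. Attachment 1 keeps version-specific rows (for example 3, 3.1 and 3.2), and the documents supplied do not give the wording of the criterion under Amendment 6. The figure could belong to an earlier version.
- A reader might take the Amendment 6 citation in SAP 1 as proof that the threshold is out of date. The SAP Amendment 1 history says the re-treatment section was aligned with Amendments 6 and 7, so the citation does not settle the origin.

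**Conclusion.** The contradiction holds: a ten-fold (1 log10) difference between row 53.1 and every other statement of the same trigger in the two documents. Its consequence is confined to values above 100,000 and up to 1,000,000 IU/mL that were not sustained over at least 4 weeks and met no other criterion in rows 53 to 56. Such a missed restart has no criterion-specific deviation code.

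The effect on efficacy results is probably very small. That judgement assumes that the reported count of one participant off NA at consolidation Week 12 is close to the number exposed, and it also relies on the conditional exclusion and the descriptive per-protocol analysis. The reason to act is consistency and correct coding of a safety rule, not an expected shift in the response estimate. Whether the figure in row 53.1 is an error or a remnant of an earlier amendment cannot be decided from the documents, and no view is taken on which threshold is clinically right.

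**What to change.** Reconcile row 53.1 with protocol 6.6.2 and SAP 5.3.1.1.2.2. If the sponsor's records show that the row was mis-stated, correct it. If it reflects the criterion in force under an earlier amendment, keep it with that version named and add a row for the current one. Then repeat the deviation check for all off-NA HBV DNA values between the two figures, and record the classification of any missed restart before the per-protocol set is fixed. Attachment 1 already provides for an update before the primary analysis database lock.

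The cost is one edited or added row and a re-check of what appear to be very few participants. Updating the protocol amendment cited in SAP 1 is separate housekeeping that can go into the same revision.

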**Per protocol analysis set (PP):** All participants in the ITT analysis set who do not have any of the selected major protocol deviations that may affect the assessment of efficacy in terms of the primary endpoint at 24 weeks after stopping all study interventions of the consolidation phase. The selected major protocol deviations for efficacy analysis purposes that will be used to identify the participants included in the PP set are described in Section 4.5 and [Attachment 1: Selected Major Protocol Deviations for Analysis Purposes](#). Participants will be analyzed according to the study intervention they were randomly assigned to.

**Pharmacokinetics analysis set (PK):** The PK analysis set is defined as subjects who have received at least 1 dose of any of the study interventions and have at least 1 valid blood sample drawn for PK analysis.

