#### **4.5. Protocol Deviations**

Only major protocol deviations will be summarized by cohort, combined cohort and overall.

Major protocol deviations will be based on clinical review, but not limited to, the following criteria: (1) entered but did not satisfy inclusion/exclusion criteria, (2) received wrong treatment or incorrect dose, (3) received a disallowed concomitant treatment, (4) efficacy not done at schedule visit, (5) developed withdrawal criteria but not withdrawn, (6) other. Protocol deviations will be closely monitored during the execution of the study and the final set of protocol deviation criteria will be finalized before the primary analysis database lock.

All major protocol deviations will be tabulated by coded term by cohort for the Treated, and ITT analysis set. A listing of the major protocol deviations will be also presented.

A subset of major protocol deviations that may affect the assessment of efficacy (see list in [Attachment 1: Selected Major Protocol Deviations for Analysis Purposes](#) ) will be identified and finalized prior to the primary database lock to define the Per-Protocol analysis set (Section [2.3](#)). The number and percentage of ITT participants who are included in the PP analysis set will be summarized, accompanied by number and percentage of ITT participants who are excluded from the PP analysis set with the incidence of the major protocol deviations.

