### **5.2.4. Per-Protocol Analysis**

The analysis of the primary efficacy endpoint will be performed on the PP set, as defined in Section 2.3, using observed case data.

The proportion of responders will be summarized descriptively using the number and percentage of participants by cohort.

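### Rows 53 to 56 of the SAP's deviation list let membership of the per-protocol set depend on the participant's course after NA was stopped

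*SAP*

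**What the plan says.** SAP 2.3 defines the PP set as "All participants in the ITT analysis set who do not have any of the selected major protocol deviations that may affect the assessment of efficacy", and SAP 5.2.4 adds that "The analysis of the primary efficacy endpoint will be performed on the PP set", with observed cases and number and percentage only. The deviations that count are in SAP Attachment 1.

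Rows 53 to 56 of that attachment share one structure: an event that calls for NA to be restarted, combined with NA not being started.

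- Rows 53 and 53.1: declining liver function, with a high HBV DNA value added as an alternative in 53.1.
- Row 54: "Participant has confirmed HBeAg seroreversion but did not start NA treatment".
- Rows 55 and 55.1: a confirmed rise in both HBV DNA and ALT without NA.
- Row 56: "Participant has a confirmed post-treatment increase in HBV DNA >20,000 IU/mL over a period of at least 4 weeks", again without NA being started.

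All are coded as wrong treatment or incorrect dose. For each, the entry on PP exclusion is "If classified as major protocol deviation, excluded from PP set". SAP 4.5 says the subset of deviations "will be identified and finalized prior to the primary database lock to define the Per-Protocol analysis set".

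SAP 5.2.2 states the responder rule: a participant who requires NA re-treatment at any time before FU Week 24 is a non-responder. SAP 5.3.1.1.2.2 and protocol 6.6.2 list the restart criteria that these rows mirror.

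**The concern.** A PP set is meant to show the result in participants who were eligible and treated as planned. By the time a restart criterion can be met, JNJ-3989 and PegIFN-α2a are over and NA has been stopped. Not restarting NA then says nothing about whether the regimen under test was delivered. The first half of each row is an unfavourable post-treatment event, and a participant who stays well cannot meet it. Two participants with the same relapse can therefore be handled differently: the one who restarts NA stays in the PP set as a failure, while the one who does not may be removed.

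The classification as major is made with the outcome in view. The study is open-label and the list is fixed only before the primary lock. Protocol 4.2 also asks that the restart decision be discussed with the sponsor. The group is foreseeable, because SAP 5.3.2.1.1.2 plans a cross-tabulation of restart criteria met or not met against NA restarted or not.

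What is at stake is the value of the PP summary as support for the primary result. If it differs from ITT, the difference may reflect who relapsed without restarting rather than adherence to the regimen.

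**Working it through.** **The plan's own figure.** SAP 1.4 and protocol 9.2 give 15 responders of 30 in Cohort 2, with a Clopper-Pearson 90% CI of 0.339 to 0.661 and width 0.322. The limits are the 5% quantile of Beta(15, 16) and the 95% quantile of Beta(16, 15). They come to 0.3389 and 0.6611, width 0.3222, so the figure reproduces. The 30 is 33 × 0.9 = 29.7, rounded.

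**Inputs.** n = 30 and x = 15 from the planning scenario. k is the number of participants removed under rows 53 to 56. The documents give no k, so 1, 3 and 5 are assumed.

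**Events before FU Week 24.** Those removed are non-responders under SAP 5.2.2. The PP rate moves from x/30 to x/(30 − k), a change of x·k / [30·(30 − k)].

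| x | Kept as non-responders | k = 1 | k = 3 | k = 5 |
|---|---|---|---|---|
| 15 | 50.0% | 15/29 = 51.7% | 15/27 = 55.6% | 15/25 = 60.0% |
| 9 | 30.0% | 9/29 = 31.0% | 9/27 = 33.3% | 9/25 = 36.0% |
| 1 | 3.33% | 1/29 = 3.45% | 1/27 = 3.70% | 1/25 = 4.00% |
| 0 | 0% | 0% | 0% | 0% |

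Check for x = 15, k = 3: 15 × 3 / (30 × 27) = 45/810 = 5.6 percentage points.

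**Events after FU Week 24.** The rows carry no time limit. SAP 3.3.2 allows the primary analysis to include later visits of participants who have reached them. A Week 24 responder who later meets a row could be removed: (15 − 1)/(30 − 1) = 14/29 = 48.3%, a fall of 1.7 points.

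**What the documents say about actual numbers.** The rationale table of SAP Amendment 4 reports one participant who met the NA completion criteria and stopped NA at consolidation Week 12. It does not name the cohort, so 30 is kept as an assumed denominator. If the endpoint is read strictly (all interventions stopped), that participant is both the only possible responder and the only person these rows can catch by the planned route.

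- Caught before FU Week 24: 0/30 becomes 0/29, which is 0% either way.
- Caught before FU Week 24, with one other responder who stopped NA by another route: 1/30 = 3.33% becomes 1/29 = 3.45%, a rise of 0.11 points.
- A Week 24 responder caught afterwards: 1/30 = 3.33% becomes 0/29 = 0%.

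Other routes off NA exist (the ALT note in protocol 6.6.1 and early discontinuation in protocol 7.1), but the documents give no count for them.

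**The case against.** The best defence is that the rows describe a departure from a protocol rule, and the SAP codes them as a treatment deviation. On that view the PP set covers adherence to the whole protocol, including the restart rule. Relapse alone removes nobody, removal needs a further decision that the deviation is major, ITT is the primary set, and the PP summary is descriptive with no test attached.

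Much of this stands. A reader might infer that the plan drops relapsers as a class. It does not: those who restart NA are not caught by these rows and remain as non-responders. A reader might also infer that no responder can be removed, so that the PP rate can only equal or exceed the ITT rate. The documents do not support that either, because the rows have no time limit and a Week 24 responder with a later event could be dropped. In addition, HBV DNA, HBeAg and liver function are not components of the endpoint in SAP 5.2.1. A participant could meet a row while HBsAg-negative and off NA, which looks like a response under 5.2.1 but is a non-response under the re-treatment wording of 5.2.2.

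What does not stand is that the conditional wording protects the analysis. It moves the choice to a judgement made with the outcome known. The adherence argument also concerns management after relapse, not delivery of the regimen that the endpoint evaluates.

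**Conclusion.** The point holds in a limited form. Rows 53 to 56, where classed as major, make PP membership depend on post-treatment outcome. Before FU Week 24 the effect is nil or upward: 1.7 points for one exclusion and 5.6 points for three at 15/30. After FU Week 24 it can be downward, to 48.3% in the same scenario. These sizes rest on assumed counts, on the planning denominator of 30, and on reading the re-treatment clause of SAP 5.2.2 as covering anyone who meets a restart criterion.

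With one participant reported off NA at consolidation Week 12, the realised effect is probably near zero. The ITT primary analysis does not change. The reason to act is that the PP definition should be defensible whatever the result, and the change is small.

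**What to change.** In SAP Attachment 1, set the entry on PP exclusion to No for rows 53, 53.1, 54, 55, 55.1 and 56. Keep the rows as reported deviations. State in SAP 5.2.4 that these participants are classified in the PP analysis by the rule in SAP 5.2.2. This takes a few table entries and one sentence, and alters no procedure or data collection. The downside is a possibly slightly lower PP rate.

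One further inconsistency needs attention in the same rows. Row 53.1 uses HBV DNA >1,000,000 IU/mL, whereas SAP 5.3.1.1.2.2 and protocol 6.6.2 use >100,000 IU/mL. These passages must be reconciled; which value is intended is for the sponsor to state.
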